3.3.5.2 Procedures for discontinuation

Patients who discontinue should always be asked about the reason(s) for their discontinuation and the presence of any adverse events. If possible, they should be seen and undergo the procedures and assessment of the Follow-up visit (Visit 5). Adverse events should be followed up; diary cards and investigational products should be returned by the patient.

3.3.5.3 Procedures for handling incorrect enrolled patients

Patients not meeting the inclusion/exclusion criteria for a study should under no circumstances be enrolled. There can be no exceptions to this rule.

-Where patients not meeting the study criteria are randomised in error or where patients subsequent to randomisation fail to meet the criteria for the study, the Principal Investigator should be informed, and the patient withdrawn from the study as soon as possible, unless there are sufficient ethical or safety reasons that the patient should remain in the study. The decision on how to proceed will be documented.

3.3.5.4 Procedures for discontinuation from genetic aspects of the study

Patients who discontinue from the study should always be asked specifically whether they are withdrawing or continuing their consent for this genetic research. It must be established whether the patient:

• Agrees to the genetic sample and any DNA extracted from the sample being kept for genetic research in the future.

Formatted: Bullets and Numbering

• Withdraws consent for the sample to be kept for genetic research in the future and wishes the sample to be destroyed. Destruction of the sample (or the DNA extracted from the sample) will only be possible so long as the particular sample is traceable. In the event that genetic research has already been performed, AstraZeneca will retain the results and associated data for regulatory reasons but these will not be used in any subsequent analyses.

The principal investigator is responsible for providing written notification to AstraZeneca of any patient who has withdrawn consent for the use of the sample taken for genetic research. AstraZeneca will provide written confirmation to the investigator of the actions taken with the sample, which must be filed in the investigator study file.

3.4 Treatments

3.4.1 Identity of investigational product and comparators

AZD9668 will be provided as a tablet for oral administration and with a matching placebo. Tablets of AZD9668 will be provided in the strength of 30 mg.

Investigational product	Dosage form and strength	Manufacturer	Formulation number	Batch number
AZD9668	Tablet, 30 mg	AstraZeneca R&D,	1756-1	Will be detailed in the Clinical study report (CSR)
Placebo AZD9668	Tablet, not applicable	AstraZeneca R&D,	P1756-0	Will be detailed in CSR

Table 2Identity of investigational product

The composition of the tablets is 30 mg AZD9668 (corresponding to 39.5 mg AZD9668 tosylate).

Excipients: cellulose microcrystalline, calcium hydrogen phosphate dihydrate, crospovidone, sodium laurilsulfate, sodium stearyl fumarate.

The drug product consists of white to off white, plain oblong, biconvex tablet. The nominal tablet weight is 400 mg.

Placebo tablets to match AZD9668 tablets contain the following excipients: cellulose microcrystalline and sodium stearyl fumarate

3.4.2 Doses and treatment regimens

In the current study the daily dose will be 120 mg (i.e. 60 mg b.i.d), except for days 1 and 14 when patients will receive only the morning dose to allow assessment of PK. This dose has been chosen as a dose that is predicted to achieve trough steady state therapeutic plasma concentrations of 19 nM (predicted from an in vivo mouse acute lung injury model) in all patients, whilst ensuring that the predicted geometric mean $C_{max,ss}$ and $AUC_{(0-24)ss}$ are below the HELC limits. The estimated margins to the HELC limits are 2.6 and 1.4 for $C_{max,ss}$ and $AUC_{(0-24)ss}$, respectively, in the fasted state. If a dose of 60 mg b.i.d is not tolerated by an individual patient then his/her dose may be halved to 30 mg b.i.d for the remainder of the study, at the investigator's discretion. The population PK model predicts that this will still achieve trough steady state plasma concentrations above 19 nM in all patients.

For morning doses administered on Days 1, 7 and 14, patients will be fasted from midnight the night before dosing except water for thirst. The patients may consume water up to 1 hour before dosing. The dose will be administered with 240 mL of water, and the patients must drink all the water. The patients must not consume any further fluids or food for a minimum of 2 hours post dose. At this time the patients will be allowed a light breakfast. Fasting the patients prior to receiving their morning dose on days when they are having ECG measurements ensures that the ECG measurements can be taken when C_{max} is maximised. There is no requirement to restrict food consumption before or immediately after administration of the remaining doses. These doses can be administered with approximately 100 mL water.

The morning and evening doses will be filled individually in high-density polyethylene (HDPE) bottles with a child resistant cap according to the random scheme. All bottles for morning and evening dose for 14 days will be packed in a white box for each patient.

At Visit 2, the required number of bottles needed for the morning and evening dose until Visit 3 will be handed over to the patient after the 4th dose has been taken in the CPU.

At Visit 3, the required number of bottles until Visit 4 will be handed over to the patient after the morning dose has been administered.

At Visit 4, the patient will be administered the morning dose in the CPU by the staff.

[figure not shown]
3.4.3 Labelling

The packaging and labelling will be performed by

AstraZeneca R&D All supplies and labels will be prepared in accordance with Good Manufacturing Practice (GMP) and local regulatory guidelines. The labels will fulfil GMP Annex 13 requirements for labelling.

3.4.4 Storage

All investigational products must be kept in a secure place under appropriate storage conditions. A description of the appropriate storage & shipment conditions are specified on

the investigational product label. The storage location will be locked and only accessible to authorised site personnel.

3.4.5 Accountability

The medication provided for this study is for use only as directed in the protocol. All unused study drugs will be accounted for and destroyed/returned appropriately by CPU personnel. The study site personnel will account for all drugs dispensed and returned. Certificates of delivery and return must be signed.

The investigator is responsible for maintaining study drug accountability at site.

3.5 Method of assigning patients to treatment groups

Informed consent will be obtained before enrolment and the patients identified with an enrolment number.

Patient eligibility will be established before treatment randomisation. Patients will be randomised strictly sequentially, as patients are eligible for randomisation. Patients fulfilling the eligibility criteria will be assigned randomisation codes (unique subject numbers), starting with 001. Numbers will be allocated in ascending order. If a patient discontinues from participation in the study, the patient number will not be re-used, and the patient will not be allowed to re-enter the study.

3.6 Blinding and procedures for unblinding the study

3.6.1 Methods for ensuring blinding

AZD9668 and placebo tablets are manufactured to appear similar in size, shape, weight and colour.

3.6.2 Methods for unblinding the study

Individual treatment codes, indicating the treatment randomisation for each randomised patient, will be available to the investigator(s) or pharmacists at the study centre.

A copy of the randomisation scheme will be made available to the pharmacist, the analyst of AZD9668 in sputum and the PK analyst to enable analysis of samples from patients who have received active treatment to be prioritised. This documentation will be placed in a secure location until the end of the study.

The treatment code must not be broken except in medical emergencies when the appropriate management of the patient necessitates knowledge of the treatment randomisation. The codes may also be unblinded, after consultation with the Drug Safety Physician at AstraZeneca, if 2 or more patients meet the discontinuation criteria as specified in Section 3.3.5.1. The investigator(s) must document and report to AstraZeneca any breaking of the treatment code. AstraZeneca retains the right to break the code for SAEs that are unexpected and are suspected to be causally related to an investigational product and that potentially require expedited reporting to regulatory authorities.

Treatment codes will not be broken for the planned analyses of data until all decisions on the evaluability of the data from each individual patient have been made and documented.

3.7 Pre-study, concomitant and post-study treatments

Patients are allowed to continue long-Acting muscarinic antagonist (LAMA), long-acting beta agonists (LABA), LABA/ICS (inhaled corticosteroids) combinations unchanged throughout the study if they are already on these. They would only need to withhold LAMA/LABA for 12 hours, and short-acting beta agonists (SABA) for 4 hours before the days on which they have their pulmonary function tests. After they have had the test they could take their normal dose of the medication. Other respiratory medications could be continued unchanged.

The following drugs (substrates for CYP2C9) will not be allowed throughout the dosing period:

- Anti-diabetics/hypoglycaemics
- Anti epileptics/anticonvulsants
- Warfarin
- Fluvastatin
- Celecoxib
- High dose continuous non-steroidal anti-inflammatory drugs (NSAIDs)
- Torsemide
- Amitryptiline
- Fluoxetine

Any other drugs including inhaled and oral respiratory drugs could be allowed provided their doses have been stable for at least 4 weeks before enrolment and the doses remain unchanged throughout the study. SABA and/or SAMA may be taken as needed for symptomatic control of breathlessness.

Other medication, which is considered necessary for the patient's safety and well-being, may be given at the discretion of the investigator. The administration of all medication (including investigational products) must be recorded in the appropriate sections of the **section**.

3.8 Treatment compliance

Treatment compliance will be checked by counting the returned medication on Day 7 and 14. In addition for the patients receiving active drug, the blood concentration of AZD9668 will serve as control.

Patients will be asked to return their unused medication and all packaging (even if empty) to the study centre at each visit for reconciliation purposes.

4. MEASUREMENTS OF STUDY VARIABLES AND DEFINITIONS OF OUTCOME VARIABLES

4.1 **Primary variable**

For description of primary variables refer to Section 4.5, pharmacokinetic, and Section 4.7, safety variables and measurement.

4.2 Screening and demographic measurements

- Demographic data, i.e. date of birth, sex, height, weight, BMI, race
- A standard medical and surgical history and a physical examination including the cardiovascular and respiratory systems
- Use of nicotine
- Concomitant medication
- Standard clinical chemistry (including FSH at Visit 1 for female patients) and haematology assessments and a mid-stream urine sample for urinalysis, and drugs of abuse screen (and pregnancy test in female patients)
- A resting blood pressure and pulse measurement (supine).
- An alcohol screen (urine test)
- A 12-lead ECG
- Hepatitis B surface antigen, Hepatitis C antibody and HIV status
- Spirometry (lung function)

4.3 Patient-Reported Outcomes (PROs)

[figure not shown]
Not applicable.

4.4 Health Economic measurements and variables

Not applicable.

4.5 Pharmacokinetic measurements and variables

For timing of individual samples refer to the detailed study plan (Table 1).

The methods for collection of biological samples and derivation of pharmacokinetic variables are presented below in Sections 4.5.1 and 4.5.2

4.5.1 Collection of biological samples

Blood samples (3 ml K₂EDTA) for determination of AZD9668 in plasma will be taken at the times presented in the detailed study plan (Table 1).

Blood samples will be collected, labelled and shipped as detailed in the laboratory handbook. The date and time of collection will be recorded.

Urine will be passed into a specially provided container at the times presented in Table 1. Urine samples will be collected, handled, labelled and shipped as detailed in laboratory handbook. The date and time of collection will be recorded.

Samples should be stored at -18° C or below, and analysed within the timeframe after collection for which the stability in the samples has been validated and found acceptable. Results from analyses stored longer than the period stated will not be reported.

Aliquots of sputum for AZD9668 analysis will be collected, handled, labelled and shipped as detailed in the laboratory handbook. The date and time of collection will be recorded.

Samples should be shipped to the appointed bioanalytical laboratory at pre-determined dates during the course of the study.

The methods used will be referred to in the clinical study report.

Samples will be disposed of within one month after the clinical study report has been finalised.

4.5.2 Drug concentration measurements, and derivation or calculation of pharmacokinetic parameters

Samples for determination of AZD9668 in plasma and urine will be analysed by

, on behalf of , AstraZeneca R&D , using validated methods of liquid chromatography and mass-spectrometry (LC-MS/MS). The lower limit of

quantification (LLOQ) of AZD9668 in plasma and urine will be 1.00 nM and 0.2 μ M, respectively.

The PK parameters will be calculated using non-compartmental analysis. The pharmacokinetic parameters will include:

Day 1: AUC_(0-t), AUC₍₀₋₂₄₎, AUC, t_{1/2}, CL/F, V_z/F, C₂₄, CL_R, A_e and F_e(%)

Day 7: Cmin,ss

Day 14: $C_{min,ss}$, $C_{max,ss}$, $t_{max,ss}$, $AUC_{(0-t),ss}$, $AUC_{(0-24),ss}$, $C_{24,ss}$, AUC_{ss} , $t_{1/2ss}$, CL/F_{ss} , V_z/F_s , R_{ac} , CL_R , $A_{e,ss}$ and $F_{e,ss}(\%)$

The accumulation ratio (R_{ac}) will be calculated using the following equation:

AUC(0-24),ss Day 14/AUC(0-24) Day 1.

An investigation of the AZD9668 concentrations in sputum will be conducted using a method of liquid chromatography and mass spectrometry (LC-MS/MS) based on that validated for human plasma.

The AZD9668 sputum analysis method will not be formally validated, but will be supported by investigations into the recovery and stability of AZD9668 in this matrix and each batch of samples will include QC samples to demonstrate the performance of the method.

Measurement of AZD9668 concentrations in sputum will be analysed by , AstraZeneca R&D

4.6 Efficacy and pharmacodynamic measurement and variables

4.6.1 Efficacy parameters

Not applicable.

4.6.2 Pharmacodynamic parameters

4.6.2.1 Induced sputum weight, neutrophils, hydroxyproline

Handling and processing of induced sputum will be performed according to validated methods. The handling, storing, shipping, method of analysis and prioritised order of analysis for the different parameters will be detailed in the laboratory handbook.

4.6.2.2 Biomarkers in serum, plasma and urine

Blood and urine samples for determination of serum amyloid A, hsCRP, cytokines (including but not limited to TNF- α and IL-8), desmosine in plasma and desmosine in urine will be taken at the times given in the study plan (Table 1). The handling, storing, shipping, method of analysis and prioritised order of analysis for these different parameters will be detailed in the laboratory handbook.

4.6.2.24.6.2.3 BronkoTest[©] diary card

The BronkoTest[©] sputum colour test (BronkoTest[©], Hampton Hill, UK) is used to characterise a COPD patient's normal chest-related symptoms and the changes that occur during an exacerbation. It documents the 3 key symptoms of such episodes, namely increased breathlessness, new sputum production or increased volume, and the purulent nature of the sputum.

In the dairy card, the following items will be filled in daily by the patients: Peak flow measurement, night-time symptoms, description of breathing, type, colour and amount of

--- **Formatted:** Bullets and Numbering

sputum and as well associated symptoms about well-being, frequency of coughing, occurrences of chest pain and cold or flu. In addition, the treatment and management of the COPD symptoms and intake of any antibiotics will be documented.

For Peak flow measurement, the subject will be provided with and instructed to use the APP[®] Mini-Wright Peak Flow Meter "Standard" (Beckmann, Seefeld, Germany).

During the Screening visit, the patients will receive the BronkoTest^{\circ} diary card and the Peak flow meter and be instructed how to use the Peak flow meter and how to fill in the BronkoTest^{\circ} diary card.

4.7 Safety measurements and variables

The methods for collecting safety data are described below.

4.7.1 Adverse events

4.7.1.1 Definitions

The definitions of adverse events (AEs), serious adverse events (SAEs) and other significant adverse events (OAEs) are given below. It is of the utmost importance that all staff involved in the study are familiar with the content of this section. The principal investigator is responsible for ensuring this.

Adverse event

An adverse event is the development of an undesirable medical condition or the deterioration of a pre-existing medical condition following or during exposure to a pharmaceutical product, whether or not considered causally related to the product. An undesirable medical condition can be symptoms (eg, nausea, chest pain), signs (eg, tachycardia, enlarged liver) or the abnormal results of an investigation (eg, laboratory findings, electrocardiogram). In clinical studies, an AE can include an undesirable medical condition occurring at any time, including run-in or washout periods, even if no study treatment has been administered.

Serious adverse event

A serious adverse event is an AE occurring during any study phase (ie, run-in, treatment, washout, follow-up), and at any dose of the investigational product, comparator or placebo, that fulfils one or more of the following criteria:

- Results in death
- Is immediately life-threatening
- Requires in-patient hospitalisation or prolongation of existing hospitalisation
- Results in persistent or significant disability or incapacity
- Is a congenital abnormality or birth defect

• Is an important medical event that may jeopardise the patient or may require medical intervention to prevent one of the outcomes listed above.

The causality of SAEs (ie, their relationship to study treatment) will be assessed by the investigator(s), who in completing the relevant case report form must answer "yes" or "no" to the question "Do you consider that there is a reasonable possibility that the event may have been caused by any of the following – study medication – other medication?" For further guidance on the definition of a SAE and a guide to the interpretation of the causality question, see Appendix B to the Clinical Study Protocol.

Note that SAEs that could be associated with any study procedure should also be reported. For such events the causal relationship is implied as "yes".

Other Significant Adverse Events (OAE)

OAEs will be identified by the Study Delivery Team Physician in consultation with the appropriate Global Drug Safety Physician during the evaluation of safety data for the Clinical Study Report. Significant adverse events of particular clinical importance, other than SAEs and those AEs leading to discontinuation of the patient from study treatment, will be classified as OAEs. Examples of these are marked haematological and other laboratory abnormalities, and certain events that lead to intervention (other than those already classified as serious), dose reduction or significant additional treatment. For each OAE, a narrative may be written and included in the Clinical Study Report.

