6. STATISTICAL METHODS AND DETERMINATION OF SAMPLE SIZE

6.1 Statistical evaluation – general aspects

A comprehensive Statistical Analysis Plan (SAP) will be prepared before database lock and unblinding of the data in order to avoid any potential bias due to knowledge of the treatment received. It will detail analyses to be performed and summaries to be produced for the Clinical Study Report (CSR).

All statistical summaries and analyses will be performed by using SAS[®] (Statistical Analysis system, SAS-Institute, Cary NC, USA).

Pharmacokinetic parameters will be derived by non-compartmental analysis using WinNonLin Pro Version 5.0 or higher version.

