6.4.4 Safety analysis

Examination of the following safety variables will address the primary objective to investigate the tolerability of 14 days' treatment with AZD9668. No formal hypotheses will be associated with these variables, although informal comparisons will be made between treatment groups to determine whether there appears to be any treatment-related effects: adverse events, vital signs, 12-lead ECG (overall evaluation), lung function, sputum bacteriology, safety lab data (clinical chemistry, haematology, urinalysis), physical examination and concomitant medication.

Adverse events will be analysed by means of descriptive statistics and qualitative analysis. AEs will be listed for each patient and summarised by System Organ Class and preferred term assigned to event by using MedDRA 10.0.

Concomitant medications will be classified according to the AZDD Drug Dictionary, the ATC system and the CPMP route of administration dictionary. All concomitant medications reported at entry and recorded during the study will be summarised and listed.

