9. PROCEDURES IN CASE OF EMERGENCY, OVERDOSE OR PREGNANCY

9.1 AstraZeneca emergency contact procedure

In the case of a medical emergency the Investigator may contact the Study Delivery Team Leader. If the Study Delivery Team Leader is not available, the Study Delivery Team Physician may be contacted at the AstraZeneca Research and Development site shown below.

9.2 **Procedures in case of medical emergency**

The principal investigator(s) is responsible for ensuring that procedures and expertise are available to handle medical emergencies during the study. A medical emergency usually constitutes an SAE and should be reported as such, see Section 4.7.1.1.

9.3 **Procedures in case of overdose**

- Use of study medication in doses in excess of that specified in the protocol should not be recorded in the eCRFs/pCRFs as an AE of 'Overdose' unless there are associated symptoms or signs.
- An overdose with associated SAEs should be recorded as the SAE diagnosis/symptoms on the relevant AE forms in the eCRFs/pCRFs.
- An overdose with associated non-serious AEs should be recorded as the AE diagnosis/symptoms on the relevant AE forms in the eCRFs/pCRFs. In addition, the overdose should be reported on the separate AZ "Clinical Study Overdose Report Form."
- An overdose without associated symptoms should not be recorded as an AE in the eCRFs/pCRFs. The overdose should be reported on the separate AZ "Clinical Study Overdose Report Form".

9.4 **Procedures in case of pregnancy**

In case of pregnancy the subject should be discontinued from the study and withdrawn from the treatment with investigational drug. Pregnancy itself is not regarded as an adverse event unless there is a suspicion that the investigational product under study may have interfered with the effectiveness of a contraceptive medication. However, the outcome of all pregnancies (spontaneous miscarriage, elective termination, normal birth or congenital abnormality) must be followed up, documented and reported to AstraZeneca using the Pregnancy Report and Pregnancy Outcome Report CRF modules even if the subject was discontinued from the study. The Pregnancy Report CRF is used to collect information before the outcome of the pregnancy is known; it should be completed as soon as possible after it has been identified that a patient received an AstraZeneca product during pregnancy and should be sent to AstraZeneca Clinical Drug Safety within 30 days.

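### The protocol permits other significant adverse events (OAEs) to be selected with treatment known, because the code-break rule covers only evaluability decisions

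*Protocol*

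**What the plan says.** Protocol section 4.7.1.1 defines OAEs and says who selects them and when: "OAEs will be identified by the Study Delivery Team Physician in consultation with the appropriate Global Drug Safety Physician during the evaluation of safety data", that evaluation being the one made for the clinical study report. The criterion for an OAE is clinical importance: "Significant adverse events of particular clinical importance, other than SAEs and those AEs leading to discontinuation of the patient from study treatment, will be classified" in this way. Illustrations follow: "Examples of these are marked haematological and other laboratory abnormalities, and certain events that lead to intervention", together with dose reduction and significant additional treatment. No numeric limit is attached to any of them. A narrative may be written for each OAE.

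On blinding, the last sentence of section 3.6.2 reads, in part, "Treatment codes will not be broken for the planned analyses of data until all decisions on the evaluability of the data from each individual patient"; these decisions must be complete and on record by then. Section 6.1 adds a safeguard for the analysis plan: "A comprehensive Statistical Analysis Plan (SAP) will be prepared before database lock and unblinding of the data in order to avoid any potential bias".

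On use of the data, section 6.4.4 tests no hypothesis, but "informal comparisons will be made between treatment groups to determine whether there appears to be any treatment-related effects".

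**The concern.** Choosing OAEs is the one step in adverse event handling that the protocol gives to sponsor-side physicians at the reporting stage, on a criterion that depends on opinion. Serious adverse events have listed criteria, and a discontinuation is a recorded fact. An OAE is an event that someone decides is important enough to stand out. If that person knows the arm, the same finding may be judged important on active drug and unremarkable on placebo, or the reverse.

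Tolerability is a primary objective and is judged without a formal test. In a study of this size, the events that the report chooses to highlight influence how a reader sums up the drug's tolerability before longer studies begin. Section 6.1 already recognises the risk of bias from knowing the treatment, but guards only the writing of the analysis plan against it.

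**Working it through.** No power, alpha or effect size is involved and the protocol states no figure on this point, so the check sets the sections side by side.

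1. **Who selects.** Section 4.7.1.1 names the Study Delivery Team Physician, who consults the Global Drug Safety Physician. Section 9.1 places the first of these with the sponsor: "the Study Delivery Team Physician may be contacted at the AstraZeneca Research and Development site shown below". The selection is therefore made on the sponsor's side, not by the blinded site investigator.

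2. **When.** Section 4.7.1.1 places the selection within the safety evaluation for the clinical study report. It does not say whether this comes before or after the codes are opened.

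3. **What holds the codes closed.** Section 3.6.2 makes one class of decision a condition for opening the codes for the planned analyses: whether each patient's data are evaluable. Labelling an event an OAE does not decide whether data are used, so it falls outside that condition.

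4. **Other safeguards.** Section 6.1 requires the analysis plan to precede database lock and unblinding. That covers the plan, not the classification of events. Section 3.6.2 also provides for opening codes during the study: "The codes may also be unblinded, after consultation with the Drug Safety Physician at AstraZeneca, if 2 or more patients meet the discontinuation criteria". It does not say that the physician consulted sees the codes. This passage closes no gap, and it does not show that the OAE selectors are unblinded.

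5. **Room for judgement.** Clinical importance, marked abnormalities and certain events are left without limits, so two competent physicians could select differently from the same listing.

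6. **What the label changes.** Section 4.1 refers to section 4.7, where OAEs are defined, for the primary safety variables. However, the variables compared between groups in section 6.4.4 are adverse events, vital signs, ECG, lung function, sputum bacteriology, laboratory data, physical examination and concomitant medication. OAEs are not named. Adverse events are listed by patient and summarised by System Organ Class and preferred term. They are recorded at the site with intensity and the investigator's causality rating (4.7.1.2). Laboratory values and changes from baseline are all listed and summarised (4.7.2.3), laboratory abnormalities are to be reported in the study report (4.7.1.2), and all data are listed (6.4.1). The only stated consequence of the label is that a narrative may be written.

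Steps 1 to 5 show that the text permits selection with treatment known. Step 6 confines the effect to emphasis and narrative. The study has 18 patients at 2:1, so 18 × 2/3 = 12 on active and 18 × 1/3 = 6 on placebo. With so few patients a blinded review of listings is a small task.

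**The case against.** The strongest reply is that the point rests on silence. The protocol nowhere says that OAEs are selected after unblinding. Section 3.6.2 sets the earliest moment for opening the codes, not the order of later work, and the analysis plan, which is not shown, could require a blinded review. It is true that the text permits the unblinded sequence without requiring it. But the protocol itself fixes the stage of OAE selection and the condition for opening the codes, so the gap lies between two of its own statements and can be closed there.

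A second reply is that the label decides nothing that is counted. This largely stands. OAEs are not among the compared variables, and the adverse event, serious adverse event, discontinuation and laboratory outputs are produced whatever the label says.

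Two stronger readings are tempting, and the documents do not support them:

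- **A shift in an OAE rate.** A reader might infer that one reclassified patient moves an arm's OAE percentage substantially, or that unequal flagging produces a large spurious difference between arms. The protocol plans no OAE rate, and it gives no frequency of candidate events and no flagging probability. Any such figure would describe a statistic that the study does not report.
- **A hidden laboratory imbalance.** A reader might infer that unblinded selection could create or conceal an imbalance in haematology or liver findings. The full listings and summaries in 4.7.2.3 and 6.4.1, and the reporting of laboratory abnormalities under 4.7.1.2, rule this out. The values appear by arm whether or not they are called OAEs.

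**Conclusion.** The point holds in a limited form. A judgement-based category is assigned by sponsor-side physicians at the reporting stage, and no stated rule keeps treatment concealed from them while they do it. The exposure is to which events the clinical study report singles out, and may narrate, as significant among 18 patients. No planned count, summary or listing changes, so no numerical size can be attached. It is a worthwhile low-cost improvement, not an error that threatens the tolerability conclusion.

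The verdict assumes that no document outside the protocol already requires blinded OAE selection. If the analysis plan does so, the protocol needs only wording that agrees with it.

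**What to change.** Make two changes to the protocol.

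- **Section 4.7.1.1:** replace the present timing with wording such as: *OAEs will be identified from listings that do not show treatment, and the selection will be documented before unblinding; any OAE added later will be reported as a post-unblinding addition.*
- **Section 3.6.2, last sentence:** add OAE classification to the decisions that must be documented before the codes are broken for the planned analyses.

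The same physicians do the same work on the same 18 patients, only earlier. The cost is a short review step before database lock. Events whose importance becomes clear only after unblinding can still be added, provided they are marked as such. No clinical rule changes.
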